### Additional reporting requirements

Supporters are also required to identify in IND safety reports all previous reports concerning similar adverse events and to analyze the significance of the current event in light of the previous reports.

#### **Reporting Process**

Adverse events may be submitted on FDA Form 3500A (MEDWATCH Form; see Attachment1), or in a narrative format. If supplied as in a narrative format, the minimum information to be supplied is noted above at the beginning of section 8.3. The contact information for submitting IND safety reports is noted below:

NYU Langone Health Contacts:

[contact]

AND

[name] Laura & Isaac Perlmutter Cancer Center NYU Langone Health [name]

Version: 11.0

[contact] [contact]

AND

PCC Assigned Medical Monitor

# 8.8 Reporting Procedures – Participating Investigators

In addition to reporting certain unanticipated problems and adverse events noted above to the FDA, it is the responsibility of the study supporter to report those same adverse events or findings to participating investigators at other study sites. The same materials and timeline used to report to the FDA are used for notifying participating investigators.

# 8.9 Study Halting Rules

Administration of study agent will be halted when four grade 4 AEs and/or AEs that would require permanent discontinuation of study drugs (See Section 6.1.8) determined to be "probably related" are reported to the PI and the Medical Monitor. The study supporter and PI will notify investigators immediately when the third grade 4 event is reported and enrollment screens will stop accepting new study participants. The study supporter will inform the DSMC members within 24 hours of this occurrence and will provide the DSMC with AE listing reports. The DSMC will convene an ad hoc meeting by teleconference or in writing as soon as possible. The DSMC will provide recommendations for proceeding with the study to the study supporter/NIH. The study supporter will inform the FDA of the temporary halt and the disposition of the study.

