# ADVERSE EVENT MANAGEMENT FOR NIVOLUMAB MONOTHERAPY OR FOR NIVOLUMAB IN COMBINATION WITH BMS-986253

Adverse Reaction	Severity*	Dose Modification
	Grade 2 diarrhea or colitis	Withhold dose a
Colitis	Grade 3 diarrhea or colitis	Withhold dose when single
		agent (Nivolumab
		monotherapy), Permanently
		discontinue when administered
		with additional study drug
	Grade 4 diarrhea or colitis	Permanently discontinue
Pneumonitis	Grade 2 pneumonitis	Withhold dose a
	Grade 3 or 4 pneumonitis	Permanently discontinue
	If AST/ALT is within normal	
	limits at baseline and increases	
	to more than 3 and up to 5 times	
	ULN	
Hepatitis	If AST/ALT is more than 1 and	Withhold dose b
	up to 3 times ULN at baseline	
	and increases to more than 5	
	and up to 10 times ULN	
	If AST/ALT is more than 3 and	
	up to 5 times ULN at baseline	
	and increases to more than 8	
	and up to 10 times ULN	
	If AST or ALT increase to more	Permanently discontinue
	than 10 times the ULN or total	
	bilirubin increases to more than	
	3 times the ULN	
Hypophysitis	Grade 2 or 3 hypophysitis	Withhold dose a
	Grade 4 hypophysitis	Permanently discontinue
Adrenal Insufficiency	Grade 2 adrenal insufficiency	Withhold dose a
	Grade 3 or 4 adrenal	Permanently discontinue
T 15:1 1 M 10:	insufficiency	145
Type I Diabetes Mellitus	Grade 3 hyperglycemia	Withhold dose a
	Grade 4 hyperglycemia	Permanently discontinue
Nephritis and Renal Dysfunction	Serum Cr more than 1.5 and up	Withhold dose a
	to 6 times the ULN	
	Serum Cr more than 6 times the	Permanently discontinue
	ULN	
Skin	Grade 3 rash or suspected	Withhold dose a
	Stevens-Johnson syndrome	
	(SJS) or toxic epidermal	
	necrolysis (TEN)	D " "
	Grade 4 rash or confirmed SJS	Permanently discontinue
- L PC	or TEN	Maria I I I I I
Encephalitis	New-onset moderate or severe	Withhold dose a
	neurologic signs or symptoms	

Version: 11.0

	Immune-mediated encephalitis	Permanently discontinue
	Other Grade 3 adverse reaction	Withhold dose a
	First Occurrence	
	Recurrence of same Grade 3	Permanently discontinue
	Adverse reactions	
	Life threatening or Grade 4	Permanently discontinue
	adverse reaction	
Other	Grade 3 myocarditis	Permanently discontinue
	Requirement for 10 mg per day	Permanently discontinue
	or greater prednisone or	
	equivalent for more than 12	
	weeks	
	Grade 2 or 3 adverse reactions	Permanently discontinue
	lasting 12 weeks or longer	

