## 8.2.2 Relationship to Study Agent

The clinician's assessment of an AE's relationship to study agents (drug,) is part of the documentation process, but it is not a factor in determining what is or is not reported in the study. If there is any doubt as to whether a clinical observation is an AE, the event should be reported. All AEs must have their

Version: 11.0

relationship to study agent assessed. In a clinical trial, the study product must always be suspect. To help assess, the following guidelines are used.

Related – The AE is known to occur with the study agent, there is a reasonable possibility that the
study agent caused the AE, or there is a temporal relationship between the study agent and event.
Reasonable possibility means that there is evidence to suggest a causal relationship between the
study agent and the AE.

Not Related – There is not a reasonable possibility that the administration of the study agent
caused the event, there is no temporal relationship between the study agent and event onset, or
an alternate etiology has been established.

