#### Report Promptly, but no later than 5 working days:

Researchers are required to submit reports of the following problems promptly but no later than 5 working days from the time the investigator becomes aware of the event:

- Unanticipated problems including adverse events that are unexpected and related
  - Unexpected: An event is "unexpected" when its specificity and severity are not accurately reflected in the protocol-related documents, such as the IRB-approved research protocol, any applicable investigator brochure, and the current IRBapproved informed consent document and other relevant sources of information, such as product labeling and package inserts.
  - Related to the research procedures: An event is related to the research procedures if
    in the opinion of the principal investigator or supporter, the event was more likely
    than not to be caused by the research procedures.
  - Harmful: either caused harm to subjects or others, or placed them at increased risk

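### The halting rule in section 8.9 is internally inconsistent: an undefined attribution term, different events counted at three and at four, and a wrong cross-reference

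*Combined protocol and SAP*

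**What the plan says.** The rule has two steps, both in section 8.9.

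- **Dosing halt.** "Administration of study agent will be halted when four grade 4 AEs and/or AEs that would require permanent discontinuation of study drugs" and determined to be 'probably related' have been reported to the principal investigator (PI) and the Medical Monitor. For the discontinuation events it points to section 6.1.8.
- **Earlier step.** The supporter and the PI will "notify investigators immediately when the third grade 4 event is reported and enrollment screens will stop accepting new study participants". The next sentence reads "The study supporter will inform the DSMC members within 24 hours of this occurrence". The section ends with an ad hoc DSMC meeting, its recommendation, and notice of the temporary halt to the FDA.

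Attribution is defined elsewhere. Section 8.2.2 requires every AE to be assessed for relationship and gives two levels. Related includes the case where "there is a temporal relationship between the study agent and event". Not Related opens with "There is not a reasonable possibility that the administration of the study agent" and adds absence of a temporal link or an established alternative cause. The dose-limiting toxicity (DLT) rule in section 5 uses 'related'. For prompt IRB reporting, section 8.4 calls an event related if "in the opinion of the principal investigator or supporter, the event was more likely" than not to have been caused by the research procedures.

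The permanent-discontinuation events are in the 6.1.7 table. They include "Grade 3 or 4 pneumonitis" and "Grade 3 myocarditis". Section 6.1.8 is Duration of Therapy.

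**The concern.** A stopping rule should give the same count, and so the same action, to anyone applying it to the same events. Here the attribution filter is undefined, so two careful readers can include different events. The early warning and the halt also count different things, so the warning need not come before the halt it is meant to anticipate.

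This is the only numeric stopping rule that runs across the whole trial, and safety of the combination is part of the primary objective. The DLT rule in section 5 covers the first six patients per arm for four weeks. Its trigger for lowering the dose or dropping the arm is limited to toxicities not already described for nivolumab alone, so it does not replace a running count.

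**Working it through.** The protocol gives no operating characteristics for section 8.9, so there is no figure to reproduce. The check compares the sections.

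**1. Attribution.** 'Probably related' appears only in section 8.9. The other terms are Related and Not Related (8.2.2), 'related' (section 5), 'possibly related' (8.1.3 and 8.4.1) and 'more likely than not' (8.4). None is stated to be its equivalent. The AE form is not in the documents, so whether it carries a further level cannot be checked.

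**2. Event sets.** Six entries in the 6.1.7 table make a named grade 2 or 3 event a permanent discontinuation:

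- grade 3 diarrhea or colitis when nivolumab is given with another study drug
- grade 3 pneumonitis
- grade 3 adrenal insufficiency
- grade 3 myocarditis
- recurrence of the same grade 3 reaction
- grade 2 or 3 reactions lasting 12 weeks or longer

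All of these can count towards the halt. None counts at the step at three. Applying both steps literally:

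| Events so far | Grade 4 count (step at three) | Halt count (step at four) | Result |
|---|---|---|---|
| Four grade 3 pneumonitis or myocarditis AEs, all 'probably related' | 0 | 4 | Dosing halts; the step at three never fires |
| Three grade 4 AEs, all unrelated | 3 | 0 | Enrolment stops; nothing counts towards the halt |
| Four grade 4 AEs, Related on timing alone | 4 | 4 if 'probably related' means Related; 0 if it means 'more likely than not' and none is judged so | Halt or no halt, depending on the reader |

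**3. Cross-reference.** Section 6.1.8 contains no discontinuation list. It mentions AEs that require dose modification and itself points to 6.1.7.

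**Illustration A: order of the two steps.** Let f be the share of halt-countable events that are grade 4. The documents give no value, so f is assumed. The fourth counted event comes before the third grade 4 event if at most two of the first four are grade 4:

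P = 1 − [4f³(1−f) + f⁴]

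- f = 0.25: 1 − (0.0469 + 0.0039) = 0.949
- f = 0.50: 1 − (0.2500 + 0.0625) = 0.688
- f = 0.75: 1 − (0.4219 + 0.3164) = 0.262

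Unrelated grade 4 events would lower these values, because they advance only the step at three.

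**Illustration B: sensitivity to the attribution reading.** Section 2.4.1 reports 13 toxicity discontinuations in a nivolumab study of 154 patients, so p = 13/154 = 0.0844. This is a proxy for the section 8.9 event set, not a measurement of it. Assume 50 treated participants, at most one event each, and no added harm from the combination. With X binomial(50, p):

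- all proxy events count: P(X ≥ 4) = 0.618 (0.194 to 0.933 over the exact 95% interval for p, 0.0457 to 0.1400)
- three quarters count: P(X ≥ 4) = 0.391
- half count: P(X ≥ 4) = 0.160
- step at three on the wider event set, all counting: P(X ≥ 3) = 0.805

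Both illustrations depend on their assumptions. The inconsistency is in the text and needs neither.

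**The case against.** **The rule can still be operated.** The PI and the Medical Monitor receive the counted events and can judge whether each is probably related. That stands. A reader might infer that the rule cannot be applied, or that the attribution is not recorded at all. The documents do not support either: they show only that the term is undefined, and the form is not available.

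**'Third grade 4 event' may be shorthand for the third counted event.** This is a reasonable guess at the intent, but the text does not say so, and the halt sentence names two kinds of event where this one names one.

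**Missing the step at three costs little.** When four discontinuation events occur, the stronger action, stopping dosing, still fires. What is lost is advance notice and an explicit enrolment stop. This stands and limits the severity. A reader might also infer that the DSMC would not hear of such a halt. That is strained, since the section runs on to a DSMC meeting and FDA notice of the halt. The 24-hour notice is only loosely worded, because 'this occurrence' follows the grade 4 sentence.

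**Other oversight exists.** The Medical Monitor reviews all AEs (8.10), SAEs are reported within 24 to 72 hours (8.4.2, 8.5), the PI's team evaluates AEs monthly (section 12), and the DSMC meets at least quarterly with reports covering dose modifications and AEs (8.10, 9.1). This is real but partial cover, since none of it supplies a numeric trigger.

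**The enrolment step may be moot.** Fresh biopsies are an entry requirement (5.1), and section 7.2.4 says no samples will be collected as of February 2024. That suggests accrual has ended, though the protocol does not say so.

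**Conclusion.** The concern holds as an inconsistency within section 8.9. The attribution term is undefined, the two steps count different events, and the citation is wrong. The second part matters most. The third is clerical, because 6.1.8 leads the reader to 6.1.7.

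Severity is minor to moderate. The conclusion rests on a literal reading of section 8.9 against 8.2.2 and the 6.1.7 table and on no assumed rate. If accrual has ended, what remains is the dosing-halt and notification wording for participants still on treatment.

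The probabilities above might tempt a reader to conclude that a threshold of four is wrong, or that counting should be confined to Arm 2. The documents do not support that. The rates are a proxy or assumed, and both the threshold and study-wide counting are trade-offs for the DSMC and the sponsor.

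**What to change.** Amend section 8.9 as follows.

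1. Cite 6.1.7.
2. Count 6.1.7 permanent-discontinuation AEs as well as grade 4 AEs at the step at three, as at the halt at four.
3. State that the 24-hour DSMC notice applies to both steps.
4. Tie attribution to one defined level. Either use Related as in 8.2.2, or keep 'probably related', define it by the 'more likely than not' standard in 8.4 (reworded to refer to study drugs, since 8.4 refers to research procedures), and record it. The DSMC and the sponsor should choose.
5. State whether several events in one participant count once. The present rule counts AEs and does not say.

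**Cost.** The change is wording in one section, with IRB approval of the amendment. Using Related needs no new data, because relationship is already captured for every AE (8.2.2, 8.3). The stricter option may need one field on the AE form if it has none.

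**Downsides to accept openly.** The wider event set makes the step at three fire more often. Related admits events linked by timing alone, so the halt becomes more sensitive and temporary pauses more likely; Illustration B gives the direction, not a forecast. An attribution filter at the step at three would remove unrelated grade 4 events that now count there. If that protection is wanted, leave the grade 4 part of that step unfiltered and say so.

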# 8.10 Safety Oversight

A Medical Monitor will be appointed to advise the study investigators and will monitor participant safety. The role of the Medical Monitor is to 1) Review all AEs on a regular basis throughout the trial; 2) be available to advise the investigators on trial-related medical questions or problems, and 3) evaluate cumulative participant safety data and make recommendations regarding the safe continuation of the study.

All Internal SAEs reported by the CTO, occurring to patients on clinical trials that are not monitored by any other institution or agency, are reported via email: [contact] and reviewed within 48 hours by the medical monitor. Based on the review, one of three determinations will be made:

- SAE report is considered to be adequate
- Queries for clarification to PI regarding treatment attribution and/or resolution of SAE or completeness of other information. The committee may request a cumulative review of all SAEs on the study to date.
- Request for full DSMC committee review of protocol at the next scheduled meeting.

The DSMC Coordinator will record the committee's decision and incorporate it into the study summary for the next scheduled study review.

Version: 11.0

Safety oversight will be under the direction of a DSMC composed of individuals with the appropriate expertise, including clinical investigators/oncologists, biostatisticians, nurses, and research administration staff knowledgeable of research methodology and design and in proper conduct of clinical trials. The DSMC will meet at least quarterly to assess safety and efficacy data on each arm of the study. The DSMC operates under the rules of an approved charter. The DSMC will provide its input to Bristol-Myers Squibb.

# 9 Clinical Monitoring

Clinical site monitoring is conducted to ensure that the rights and well-being of human subjects are protected, that the reported trial data are accurate, complete, and verifiable, and that the conduct of the trial is in compliance with the currently approved protocol/amendment(s), with GCP, and with applicable regulatory requirement(s).

It is the responsibility of the Principal Investigator to oversee the safety of the study. This safety monitoring will include careful assessment and appropriate reporting of adverse events as noted above, as well as the construction and implementation of a site data and safety-monitoring plan. Serious adverse events are evaluated regularly by the principal investigator in conjugation with the research team, the DSMC is notified of serious adverse events via email initially, reviewed offline by the designated medical monitor, and presented at the next DSMC monthly meeting. The Data Safety and Monitoring Committee (DSMC) will review the study at least quarterly. Medical monitoring will include a regular assessment of the number and type of serious adverse events.

#### 9.1 Data Monitoring Committee

This investigator-initiated study will be monitored by the Data Safety Monitoring Committee (DSMC) of the New York University (NYU) Perlmutter Cancer Center (PCC). The DSMC operates based on the National Cancer Institute approved Charter. It is an existing and multidisciplinary committee (consisting of clinical investigators/oncologists, biostatisticians, nurses, and research administration staff knowledgeable of research methodology and design and in proper conduct of clinical trials) that is responsible for monitoring safety, conduct and compliance in accordance with protocol data monitoring plans for interventional clinical trials conducted in the NYULMC Perlmutter Cancer Center that are not monitored by another institution or agency. The DSMC reports to the Director of the NYULH PCC.

Per the NYU PCC Institutional Data Safety and Monitoring Plan, this phase II trial will be monitored by DSMC quarterly (from the date the first patient is enrolled), at protocol-specified interim time points, and at the completion of the study prior to study closure. This review includes accrual data, subject demographics and adverse events. Principal Investigators are required to attend the review of their studies. Additional reviews can be scheduled based on SAE reports, investigator identified issues, external information, etc. The DSMC will review safety data every 3 months. DSMC summary reports are available to facilitate the review and monitoring of this study. These reports include the following: patient listings and summary reports that describe study enrollment and accrual, eligibility, demographic characteristics, dose modifications, adverse experiences, subject's death and additional external published data if applicable to the study. Cumulative toxicities, SAEs, and AEs are reviewed, to identify possible adverse events with elevated frequency that is unexpected. Once a

Version: 11.0

recommendation is made if further action is required, the Investigator's must respond within of the time period specified in the DSMC letter.

# 10 Statistical Considerations

# 10.1 Statistical and Analytical Plans (SAP)

A formal SAP will be completed prior to database lock.

# 10.2 Statistical Hypotheses

The null hypothesis for the primary endpoint is that there is no difference in the ORR of the Nivolumab and BMS-986253 combination and the ORR of the Nivolumab monotherapy.

The null hypothesis for the secondary endpoint is that there is no difference in TTR, DOR, PFS, OS, and safety for the Nivolumab and BMS-986253 combination and the Nivolumab monotherapy arm.

The alternative hypothesis for the primary endpoint is that there is a difference in the ORR of the Nivolumab and BMS-986253 combination and the ORR of the Nivolumab monotherapy.

The alternative hypothesis for the secondary endpoint is that there is a difference in TTR, DOR, PFS, OS, and safety for the Nivolumab and BMS-986253 combination and the Nivolumab monotherapy arm.

#### 10.3 Analysis Datasets

The analysis dataset will be the Intention-to-Treat (ITT) Analysis Dataset (i.e., all randomized participants).

## 10.4 Description of Statistical Methods

#### 10.4.1 General Approach

Descriptive statistics will be provided for every covariate and outcome by the studied arms. Continuous data will be presented as means with standard deviations, and categorical data will be presented as numbers with percentages. All p-values will be two sided. Normality assumptions will be checked and log transformation will be considered if normality assumption is violated.

#### 10.4.2 Analysis of the Primary Efficacy Endpoint(s)

ORR will be defined as the best objective response using RECIST v.1.1 criteria based on MRI or CT scan evaluations following treatment. ORR will be compared by two-sample proportion test between BMS-986253 in combination with Nivolumab in comparison to Nivolumab monotherapy. P-values will be two-sided and any p-values less than 0.05 will be significant. No adjustment to significance determination for multiple comparisons will be made.

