#### 4.2.3 Exploratory Endpoints

Exploratory/translational endpoints will include detailed analysis of fresh pre-treatment and on-treatment (protocol at three months and at time of progression) core biopsies. Our collaboration team at NYU includes the ability to interrogate the TME in a novel, rigorous manner using 30-parameter platforms for single cell flow cytometry. This novel technology also has the ability to "tag" cell subsets/markers and perform single cell RNAseq. Using these techniques, we will aim to discover novel biomarkers predictive of response along with the ability to identify additional novel targets in patients who may "escape" or relapse to known immune oncology therapies.

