#### 10.4.3 Analysis of the Secondary Endpoint(s)

Secondary Endpoints, including TTR, DOR, PFS, OS, and exploratory analysis of the HCC TME, will be performed. TTR and DOR will be described and PFS and OS will be compared between subjects receiving BMS-986253 in combination with Nivolumab in comparison to Nivolumab monotherapy. Kaplan-Meier method will be used to analyze the median TTR, DOR, PFS, and OS. Categorical variables will be compared by two-sample proportion test, survival outcomes will be compared by log rank test, and continuous outcome will be compared by two-sample t-test.

Version: 11.0

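### Between-arm tumour-microenvironment comparisons have no stated baseline adjustment, and the unadjusted 0.05 rule is not clearly confined to ORR

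*Combined protocol and SAP*

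**What the plan says.** - **Significance rule.** Section 10.4.2, headed as the primary efficacy analysis, describes the ORR comparison and then states: "any p-values less than 0.05 will be significant. No adjustment to significance determination for multiple comparisons will be made". The general section, 10.4.1, sets sidedness ("All p-values will be two sided") but gives no threshold and no multiplicity rule.
- **Place of the TME analysis.** Section 10.4.3 says: "Secondary Endpoints, including TTR, DOR, PFS, OS, and exploratory analysis of the HCC TME, will be performed". Section 3.2 makes the TME a secondary objective, while section 4.2.3 places it under exploratory endpoints.
- **Test.** Section 10.4.3 assigns one test per data type. For continuous data it says: "continuous outcome will be compared by two-sample t-test". No baseline term, change score or paired model is mentioned. Section 10.4.1 adds only a possible log transformation.
- **Data.** Section 4.2.3 plans "30-parameter platforms for single cell flow cytometry" together with single-cell RNAseq, and gives the purpose as "we will aim to discover novel biomarkers predictive of response".
- **Paired sampling.** Section 5.1 requires willingness to give biopsies before and during treatment. Sections 7.2.2, 7.2.4 and 7.3.3.4 and the Schedule of Events (section 20) place them at screening and in Cycle 3.
- **Later detail.** Section 10.1 promises a formal SAP before the database is locked. No separate SAP is in the document.

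**The concern.** There are two gaps.

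First, TTR, DOR, PFS and OS are time-to-event outcomes, so the TME measures are the evident continuous outcomes in section 10.4.3. For them the plan names a test without saying whether the pre-treatment value is used. In a trial of 25 per arm, leaving out a baseline that costs a biopsy to obtain can waste precision. Leaving the choice between on-treatment values and changes open also allows it to be made after the data are seen.

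Second, the threshold sentence speaks of any p-value and of multiple comparisons, although its section describes a single ORR test. If an analyst carried it over to a high-dimensional marker set, chance differences between arms would be reported as significant.

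**Working it through.** **The plan's own power figure.** Section 10.5 gives 80% power for ORR 15% vs 49%, 25 per arm, two-sided 0.05, unpooled Z-test.

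- Standard error = √(0.15×0.85/25 + 0.49×0.51/25) = √(0.005100 + 0.009996) = 0.1229.
- Power = Φ(0.34/0.1229 − 1.96) = Φ(0.807) = 79.0%.

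The figure reproduces to within about one point. It concerns ORR only; no power or precision is stated for any TME marker.

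**Unadjusted testing.** Inputs: α = 0.05 (section 10.4.2); m independent true-null tests. The document gives no m; 30 parameters describe a platform, not a list of tests. Expected false positives = 0.05m; chance of at least one = 1 − 0.95^m.

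| m (assumed) | Expected false positives | Chance of at least one |
|---|---|---|
| 10 | 0.5 | 40.1% |
| 30 | 1.5 | 78.5% |
| 100 | 5 | 99.4% |
| 1,000 | 50 | practically 100% |

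Correlation between markers leaves the expected count unchanged but alters the chance of at least one. A Bonferroni limit for m = 30 (0.05/30 = 0.00167) would raise the difference detectable with 80% power at 25 per arm from 0.81 SD to 1.19 SD. That is why false-discovery control suits this work better.

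**Use of the pre-treatment value.** Let σ² be the common variance of pre- and on-treatment values, r their correlation within participants, and n the number of pairs per arm. Ignoring the small loss of degrees of freedom, the variance of the between-arm difference is:

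- on-treatment values only: 2σ²/n
- change from baseline: 2σ²/n × 2(1 − r)
- ANCOVA: 2σ²/n × (1 − r²)

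| r (assumed) | Change score ÷ on-treatment only | ANCOVA ÷ on-treatment only | ANCOVA ÷ change score, (1 + r)/2 |
|---|---|---|---|
| 0.3 | 1.40 | 0.91 | 0.65 |
| 0.5 | 1.00 | 0.75 | 0.75 |
| 0.7 | 0.60 | 0.51 | 0.85 |

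If all 25 per arm gave both biopsies, ANCOVA would match an on-treatment-only t-test with 25/0.91 = 27, 25/0.75 = 33 and 25/0.51 = 49 per arm. A change score loses precision against the on-treatment value when r is below 0.5.

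**Power illustration.** With 20 pairs per arm and a 0.8 SD effect (both assumed), simulation gave:

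| r (assumed) | On-treatment t-test | Change t-test | ANCOVA |
|---|---|---|---|
| 0.3 | 69% | 55% | 72% |
| 0.5 | 70% | 70% | 81% |
| 0.7 | 68% | 89% | 92% |

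**The case against.** The strongest reply is that the plan does not commit the errors a reader might infer from it.

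- **Scope of the rule.** One might infer that the plan declares every TME marker with p below 0.05 significant. It does not say so. The sentence sits under the primary-endpoint heading, and neither section 10.4.3 nor 4.2.3 repeats it. This stands: the broad reading is possible, because no other rule can be read, but it is an inference.
- **Pairing.** One might infer that the pre-treatment biopsy is ignored. A two-sample t-test on changes from baseline fits the wording equally well, so its use is unspecified rather than excluded. This stands too, but ANCOVA has lower variance than either t-test at each correlation examined.
- **False response biomarkers.** The aim in section 4.2.3 is to predict response, which is not a comparison of arms. Unadjusted arm tests do not by themselves produce false predictors of response, and ANCOVA by arm does not serve that aim. No test is stated for it.
- **Exploratory status.** Unadjusted p-values are acceptable in work reported as hypothesis-generating, and most mentions of the TME use that label. This softens the multiplicity part. It does not remove it, since section 3.2 ranks the TME as a secondary objective.
- **Text not available.** The Statistical Analysis row of the Protocol Summary breaks off in the copy read here where it turns to exploratory endpoints, so its content is unknown. A formal SAP is also still promised. Section 10.4 itself is readable and contains no such control.
- **Timing.** Sections 7.2.4 and 13.4.1 say specimen analysis was complete by February 2024, so a rule written now may follow the marker data. That calls for an honest date in the SAP; it is no reason to leave the rule unwritten.

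**Conclusion.** The point holds as a gap in specification. The readable plan names a two-sample t-test for continuous outcomes, does not say how the pre-treatment biopsy value enters, and does not confine the unadjusted 0.05 rule to ORR.

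The gain from ANCOVA depends on the assumed correlation: variance falls by 9% at 0.3, 25% at 0.5 and 49% at 0.7 relative to on-treatment values alone, so at low correlation it is small. The false-positive figures (1.5 expected, 78.5% chance of at least one) require 30 independent null tests and the broad reading of section 10.4.2. The number of tests, the number of biopsy pairs and the correlations are all assumptions.

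A reader should not conclude that the plan mandates false biomarkers or discards the baseline. Nor is the trial's main result at risk: the ORR conclusion and the sample size are unaffected.

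**What to change.** In the formal SAP:

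1. State that the unadjusted 0.05 rule applies to the ORR test only.
2. Give the TME analysis one rank, exploratory, and align sections 3.2, 4.2.3 and 10.4.3 with it.
3. For between-arm comparisons of continuous TME markers, replace the two-sample t-test with ANCOVA of the on-treatment value on arm and pre-treatment value, on the log scale where skewed. Name the biopsy that supplies the on-treatment value, since section 4.2.3 also mentions one at progression.
4. List the markers. Reduce single-cell data to one value per participant before testing, and report false-discovery-rate-adjusted values (for example Benjamini-Hochberg), separately for the cytometry panel and the RNAseq set.
5. Describe the response-prediction analysis separately, and record whether marker data had been seen when these rules were written.

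The cost is SAP wording and analysis time, with no new data. The downsides are that ANCOVA uses only participants with both biopsies, so the number of pairs per arm should be reported, and that fewer markers will be called significant.
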